2. STUDY OBJECTIVE

Primary objectives

The primary objective of this study is to assess the efficacy and safety of LMIS 25 mg for up to 24 weeks following 2 subcutaneous doses given 12 weeks apart in subjects with prostate cancer

Secondary objectives

To establish the serum PK profile of leuprolide for LMIS 25 mg in a subset of subjects with prostate cancer

To assess the ECG effects of leuprolide in relationship to plasma concentrations of both leuprolide and testosterone

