3. STUDY DESIGN

3.1 Overall Study Design

This is a multi-national, multi-center, open-label, single-arm study. All subjects will be males with prostate cancer judged to be candidates for medical androgen ablation therapy and all will receive LMIS 25 mg in an unblinded fashion. Subjects with morning serum testosterone level > 150 ng/dL at screening, adequate organ functions, ECOG performance score ≤ 2 , and have a life expectancy of at least 18 months will be eligible to enter the study.

The study duration is approximately 24 weeks. Two separate doses of LMIS 25 mg will be given to subjects by subcutaneous injection at 12 weeks apart in an unblinded manner. LMIS 25 mg will be administered on Day 0 (Visit 2) and Day 84 (Visit 13). At the end of 12 weeks (Day 84), all

Statistical Analysis Plan

subjects who have tolerated LMIS 25 mg will be administered the second dose of LMIS 25 mg and will be followed for tolerability, safety, efficacy, PK/PD parameters for another 12 weeks (Day 168/week 24).

To evaluate the sustained castration testosterone level after two doses of LMIS 25 mg injections, the first enrolled 30 subjects are considered as a subset for PK assessment and will be followed for an additional 2 weeks (Day 182/week 26) post Day 168 (week 24) to establish the extended pharmacokinetic and pharmacodynamics profiles of serum leuprolide and testosterone levels. This additional sampling is meant to assess the flexibility of the time period between doses during routine use of LMIS 25 mg.

The efficacy assessments will be performed in both ITT and PP populations. Efficacy assessment will include the percentage of subjects reached the castrate levels (≤ 50 ng/dL) of serum testosterone on Day 28 (week 4) post the first dosing of LMIS 25 mg, the effect of LMIS 25 mg on serum levels of testosterone, PSA, and luteinizing hormone (LH). The acute-on-chronic (surge) effect of serum testosterone and LH will also be monitored in all subjects. In addition, the effects of LMIS 25 mg on the percentage of subject with PSA relapse and on the percentage of subjects that achieves normal serum PSA level will be determined at the end of study.

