An analysis will be provided for the PK/ECG population based on a linear mixed effects model. The mixed-effects model will contain $\Delta QTcF$ as the dependent variable and include the corresponding leuprolide or testosterone serum concentrations in separate models with a random intercept and slope, day/time point as a categorical variable, and baseline QTcF (adjusted for the overall mean of subjects' baseline data included in the model) as the independent variables. The mixed effects model will be used to estimate, for all subjects in the PK/ECG analysis population, the predicted population mean $\Delta QTcF$ and its corresponding 2-sided 90% CI at mean C_{max} of the serum concentrations. Serum concentration values reported as below the limit of quantitation (BLQ) will be assigned a value of zero in this analysis. This analysis will be repeated for ΔHR , ΔPR , and ΔQRS , but 95% CIs will be presented rather than 90%.

Statistical Analysis Plan

The adequacy of the linear assumption between Δ ECG interval and serum concentrations will be determined by adding a quadratic term to the mixed-effects model. If the quadratic term is different than zero, having a p-value <0.05 , and an Akaike's information criteria (AIC) that is smaller in comparison to the linear model's AIC, then a quadratic term may be added. In addition, a transformation of the concentrations [e.g. $\log(\text{Concentration}/\text{LLOQ})$, where LLOQ is the lower limit of quantitation of the assay and all values below the LLOQ are replaced with the LLOQ] may also be assessed. The best model fit will be determined by the lowest AIC, unless the model results are not clinically or physiologically sensible.

If convergence cannot be reached, adjustment to the model as follows will be considered: the random slope may be removed, an alternative covariance structure attempted, or as a last resort, the removal of the time effect may be considered.

The relevant SAS code statements are:

```
PROC MIXED DATA = DATA METHOD=REML;
  CLASS SUBJID ATPTN;
  MODEL CHG = CONC ATPTN BASEADJ /NOINT SOLUTION OUTP=PRED;
  RANDOM INTERCEPT CONC /TYPE=UN SUBJECT=SUBJID;
  ESTIMATE ' $\Delta$ ECG at Cmax' CONC xx.x / CL ALPHA=0.1;
RUN;
```

In the above statements:

- CHG represents the Δ QTcF value (or corresponding secondary parameter);
- CONC represents measured serum concentrations of leuprolide or testosterone;
- ATPTN represents the day/time point;

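### The SAP lets the concentration-ECG model drop its day/time term if it does not converge; in a single-arm trial this mixes visit-wide ECG changes that track concentration with a concentration effect

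*SAP*

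**What the plan says.** SAP section 2 adds a secondary objective: "To assess the ECG effects of leuprolide in relationship to plasma concentrations of both leuprolide and testosterone". SAP 11.5 meets it with a linear mixed model for change from baseline in QTcF, repeated for HR, PR and QRS. The model takes "leuprolide or testosterone serum concentrations in separate models with a random intercept and slope", includes "day/time point as a categorical variable", and adjusts for centred baseline. The code reads "MODEL CHG = CONC ATPTN BASEADJ /NOINT SOLUTION OUTP=PRED" and "RANDOM INTERCEPT CONC /TYPE=UN SUBJECT=SUBJID".

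If convergence fails, three adjustments are listed: "the random slope may be removed, an alternative covariance structure attempted", or "as a last resort, the removal of the time effect may be considered". No condition is attached to the time-free model: it is not labelled exploratory, and no code is given for it.

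SAP 3.1 states the design: "This is a multi-national, multi-center, open-label, single-arm study".

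**The concern.** With one arm there is no untreated group to show what the ECG does at each visit for reasons other than drug or testosterone level. The random effects are by subject only. The categorical day/time term (ATPTN) therefore carries the whole job of separating a change common to all men at a visit from a change that follows concentration.

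The scheduled post-baseline ECGs are few: Day 0 at 4 hours, Day 28, Day 84 pre-dose, Day 84 at 4 hours, and Day 168 (Protocol 7.3.5; SAP Tables 3.1-1 and 3.1-2). Concentration is closely tied to these times. The protocol synopsis expects testosterone to reach castrate level within two to four weeks, so among these five points it should be high only at Day 0, 4 hours. Leuprolide is assumed here to be highest at the two 4-hour points.

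If ATPTN goes, a time-of-day shift at 4 hours can read as a leuprolide effect, and a rise from Day 28 on can read as leuprolide shortening QTcF. Protocol 5.5 lists QT/QTc prolongation among the reported adverse events of leuprolide acetate, so either error would matter to the ECG report.

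**Working it through.** The documents give no expected result, variance or power for the ECG model, so there is no stated figure to reproduce. The check has three steps.

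**1. Where a shared change goes.** Write the change for man i at time j as

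CHG_ij = b1·CONC_ij + time_j + b2·BASEADJ_i + u0_i + u1_i·CONC_ij + e_ij.

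The ESTIMATE line in the SAP code contains only CONC, so the reported quantity is b1 × mean Cmax. If time_j is omitted but a fixed intercept is present, then to a first approximation (visit means only) b1 picks up

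bias = Σ(c_j − c̄)(s_j − s̄) / Σ(c_j − c̄)²,

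where c_j is the mean concentration and s_j the shared shift at time j. Only the part of the shift pattern aligned with concentration enters.

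*Assumed inputs, not in the documents:* leuprolide means 30, 0.7, 0.4, 30, 0.4 ng/mL at the five times in order, with mean 61.5/5 = 12.3 and Σ(c_j − c̄)² = 1044.36; shifts of 8 msec.

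- Shift at the two 4-hour points only: numerator 283.2; slope 283.2/1044.36 = 0.271; × 30 = **+8.1 msec**.
- Shift from Day 28 on: numerator −141.6; slope −0.136; × 30 = **−4.1 msec**.
- The same shift at all five points: numerator 0, so **0 msec**.

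**2. Simulation with subject effects and within-visit spread.** 144 men (the number enrolled, SAP 4.4); random intercept only, which is the model after the random slope has been removed; true concentration effect zero. Further assumptions: testosterone means 450 ng/dL at Day 0, 4 hours and 12–18 later; within-subject SD 8 msec. There were only 8 runs per pattern, so the means are approximate. Entries are b1 × mean Cmax in msec, time term dropped, with a fixed intercept / with NOINT left as coded.

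| Shared shift (msec) | Leuprolide | Testosterone |
|---|---|---|
| +8 at 4-hour points | +7.9 / +8.0 | +5.2 / +5.9 |
| +8 from Day 28 on | −4.2 / −2.4 | −6.9 / −5.8 |
| Drift 0, 2, 4, 4, 8 | −2.3 / −0.8 | −4.2 / −3.1 |
| +8 at every point | +0.2 / +1.9 | +0.1 / +1.3 |

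With the time term kept, the same patterns gave −0.4 to +0.1 (leuprolide) and −1.6 to +0.7 (testosterone), against a true value of 0.

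**3. How often the 90% CI wrongly excludes zero (nominal 10%).** 400 runs per scenario, 133 men, assumed subject SD 8, residual SD 10 and baseline SD 15 msec, leuprolide elsewhere 1% to 20% of its 4-hour level, testosterone 450 then 15 ng/dL. The calculation was done twice with independent code; the ranges cover both.

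- Time term kept: 7–13% in every scenario.
- Dropped with NOINT, +2 msec at 4 hours: 76–83% (leuprolide), 53–54% (testosterone).
- Dropped with NOINT, +5 msec at 4 hours: 99–100%, with a spurious +3.7 to +5.3 msec.
- Dropped with NOINT, +10 msec at the castrate visits: leuprolide 50–93% with the wrong sign (−1.6 to −2.9 msec); testosterone 100%.
- Dropped, plain intercept restored: 44–100% under the 4-hour and castrate-visit shifts.
- Uniform +3 msec: 24–55% with NOINT; 9–10% with an intercept.

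**Convergence.** In 25 simulated data sets, the unstructured random intercept-and-slope model was flagged in 14. The random-intercept model with ATPTN converged in all 25.

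**The case against.** The clause is guarded: it applies only on non-convergence, only as the final option, and only as something to consider. The two options named before it simplify the random part, which is where such models usually fail, and the convergence check supports that. The high error rates are therefore conditional on a step that should hardly ever be reached. This stands, and it limits the point to an improvement of wording.

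A reader might infer that any shared QTcF change is credited to concentration. The calculation does not support that: a uniform shift goes into the intercept, and only the part that tracks concentration biases the slope. The leak of a uniform shift depends on NOINT staying in the reduced model. The SAP gives code only for the planned model, where ATPTN supplies the intercepts, so that is one possible reading.

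A reader might also infer that a real QTcF signal would be hidden. SAP 11.5 also requires mean change with a CI at each visit and time point, and categorical QTcF analyses at each time point and at the post-dose maximum. None of these uses the mixed model, so a shared change would still be seen there. They do not, however, correct the model's estimate at Cmax.

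Lastly, a castration-related change is what a testosterone-ECG analysis looks for, so calling it an error in the testosterone model is debatable. This stands in part. With ATPTN kept, that slope rests on differences between men within a visit and is imprecise. Dropping ATPTN does not solve this: the model then cannot tell testosterone from anything else that changed between Day 0 and Day 28.

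**Conclusion.** The point holds in a limited form. The SAP permits, without conditions, a reported model in which visit-wide changes in QTcF, HR, PR or QRS that track concentration cannot be separated from a concentration effect. The estimate at mean Cmax and its CI can then be biased in either direction, including the wrong sign for leuprolide. If NOINT is left in place, even a uniform shift leaks in.

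The direction of the bias was the same under both sets of simulation assumptions. Its size depends on concentrations, variances and shifts that the documents do not give, so the msec values and error rates above are illustrations. They describe the time-free model once it is used; they are not the error rate of the plan as a whole, and nothing in the documents suggests that the step will be needed.

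The primary efficacy criterion in SAP 9.1 is untouched. This is a cheap improvement to a secondary safety analysis.

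**What to change.** In SAP 11.5:

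- Delete the clause "as a last resort, the removal of the time effect may be considered".
- State that ATPTN stays in every reported concentration-ECG model, for QTcF, HR, PR and QRS.
- End the fallback sequence at the random-intercept model with fixed effects CONC, ATPTN and BASEADJ, rescaling CONC if that is needed for convergence.
- If a time-free model is shown at all, restore its fixed intercept (remove NOINT) and label it exploratory.

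The cost is about a sentence of SAP text, with no extra data or patients. The downside is a wider interval than the time-free model would give, most of all for testosterone, whose level is almost determined by visit. That width reflects what a single-arm trial with five post-baseline ECG times can say about concentration.

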- BASEADJ represents the numeric baseline minus the overall mean of all baseline values for the ECG parameter;
- TYPE=UN means that an unstructured covariance matrix will be used for the correlated random effects (INTERCEPT and CONC);
- xx.x in the ESTIMATE statement represents the estimated arithmetic mean C_{max} for leuprolide or testosterone.

Categorical Analyses for ECG Report

Categorical analyses of HR, PR, QRS, and QTcF will be performed to determine the number and percentage of subjects, who meet each of the following criteria at each day/time point and at the maximum/minimum QTcF (HR, PR or QRS) value postdose:

- Result QTcF ≤ 450 , >450 and ≤ 480 , >480 and ≤ 500 , and >500 msec;

Statistical Analysis Plan

- Change from baseline $\Delta\text{QTcF} \leq 30$, >30 and ≤ 60 , and >60 msec;
- PR Outliers (PR >200 msec and a 25% or greater increase from baseline);
- QRS Outliers (QRS >100 msec and a 25% or greater increase from baseline);
- HR Outliers (HR <50 beats/min and a 25% or greater decrease from baseline);
- HR Outliers (HR >100 beats/min and a 25% or greater increase from baseline).

Morphological ECG Diagnostic Statement Analyses for ECG Report

Abnormal morphological diagnostic statements will be tallied and tabulated for each day/time point and overall. The incidence rate of abnormal diagnostic statements will be tabulated for both baseline and post dose assessments, and also tabulated with abnormal diagnostic statements categorized as treatment emergent diagnostic statements (i.e., abnormal diagnostic statements not present on the baseline assessments). The variety of morphology statements with the same meaning will be aggregated into defined categories by the Cardiac Safety Expert and incorporated into the analysis dataset. For example, T-wave inversion in Lead V2 and T wave flattening in Lead II will both be categorized as nonspecific T-wave abnormality.

Adequacy of HR Correction for ECG Report

The adequacy of the correction formula for QTcF will be assessed by determining the linear relationship of QTcF interval to RR. Adequacy will be defined as a population QTcF:RR slope of $< |0.045|$, and a slope of $< |0.045|$ in at least 50% of individual subjects. If QTcF interval is determined to be an inadequate correction, the QT interval with a study specific QTcSS will be calculated.

ECOG Performance Status

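### The SAP text promises the predicted mean ΔQTcF at mean Cmax, but the coded ESTIMATE row returns only slope × Cmax

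*SAP*

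**What the plan says.** SAP 11.5, under the additional ECG and PK analyses for the ECG report, names the target: "The mixed effects model will be used to estimate, for all subjects in the PK/ECG analysis population, the predicted population mean" ΔQTcF, with a two-sided 90% CI, at mean Cmax. Leuprolide and testosterone are fitted in separate models, and the analysis is repeated for HR, PR and QRS, where "but 95% CIs will be presented rather than 90" per cent.

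The SAS template in the same section declares ATPTN (day/time point) in CLASS and then has "MODEL CHG = CONC ATPTN BASEADJ /NOINT SOLUTION OUTP=PRED". Its ESTIMATE statement, labelled as ΔECG at Cmax, has only "CONC xx.x / CL ALPHA=0.1". The notes to the code say that "xx.x in the ESTIMATE statement represents the estimated arithmetic mean" Cmax. They define BASEADJ as baseline minus the overall baseline mean. They give no weights for ATPTN.

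Two departures from the template are allowed. If the quadratic term is significant and lowers the AIC, "then a quadratic term may be added". If the model does not converge, then as a last resort "the removal of the time effect may be considered".

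**The concern.** A row with a coefficient on CONC alone is not a predicted mean in a model whose intercepts are the ATPTN coefficients. It is the part of the change that the model attributes to concentration. A change common to all subjects at a visit is left out of a number whose sentence and label both say mean change.

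The relation of ECG change to leuprolide and testosterone concentration is a secondary objective (SAP 2) and a secondary safety endpoint (SAP 3.3), and SAP 11.5 makes QTcF the primary ECG assessment of the ECG report. This row is the only model-based estimate at Cmax that the SAP specifies. SAP 1 lets the SAP override the protocol, but nothing says whether SAP text or SAP code governs when they differ. Two programmers could therefore report different numbers, each with support in the document.

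**Working it through.** The plan states no ΔQTcF, slope or Cmax, so there is no figure of its own to reproduce. The check is algebra on the coded row, followed by illustrations.

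**1. What the row estimates.** With NOINT and ATPTN in CLASS, the fixed part of the model is

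E[ΔQTcF at time t] = τ_t + β·CONC + γ·BASEADJ.

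- Coded row: CONC = Cmax, all ATPTN = 0, BASEADJ = 0. Result: β·Cmax.
- Predicted mean at mean baseline: the same row plus ATPTN weights w_t that sum to 1. Result: Σ w_t·τ_t + β·Cmax.

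The difference is Σ w_t·τ_t. Omitting BASEADJ does no harm, because it is centred. Omitting the random effects gives population-level inference, as intended. The design has full rank, so the coded row is estimable and SAS gives no warning.

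**2. Exact shift result.** The ATPTN dummies sum to a column of ones. Adding d to every response therefore adds d to each ATPTN coefficient and changes nothing else. One simulated dataset refitted with d = 0, 5, 10 and 20 ms confirms this:

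| d (ms) | Coded row | Day 0, 4 h row | Day 84, 4 h row |
|---|---|---|---|
| 0 | 8.12 | 7.90 | 6.48 |
| 5 | 8.12 | 12.90 | 11.48 |
| 10 | 8.12 | 17.90 | 16.48 |
| 20 | 8.12 | 27.90 | 26.48 |

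The coded row's 90% CI is 6.13 to 10.11 all four times.

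**3. Illustrations.** From the documents: 144 enrolled subjects (SAP 4.4), used in place of the unknown PK/ECG population, and five post-dose ECG times read from the schedule (Day 0 at 4 h, Day 28, Day 84 pre-dose, Day 84 at 4 h, Day 168; protocol 7.3.5). The rest is assumed:

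- mean leuprolide 30, 0.8, 0.4, 30 and 0.4 ng/mL at those times, CV 50%, mean Cmax 35 ng/mL;
- SDs of 6 ms (random intercept), 0.05 (random slope) and 8 ms (residual);
- slope 0 or 0.2 ms per ng/mL, so β·Cmax = 0 or 0.2 × 35 = 7 ms.

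Averages over 100 datasets per scenario, with 90% CI, all rows at Cmax:

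| Scenario | Coded row | Day 0, 4 h row | Day 84, 4 h row |
|---|---|---|---|
| A: +10 ms from Day 28, slope 0 | -0.10 (-2.20 to 2.00) | -0.12 (-1.56 to 1.32) | 9.98 (8.55 to 11.42) |
| B: slope 0.2 only | 6.90 (4.80 to 9.00) | 6.88 (5.44 to 8.32) | 6.98 (5.55 to 8.42) |
| C: A's shift and slope 0.2 | 6.90 (4.80 to 9.00) | 6.88 (5.44 to 8.32) | 16.98 (15.55 to 18.42) |
| D: +10 ms at all times and slope 0.2 | 6.90 (4.80 to 9.00) | 16.88 (15.44 to 18.32) | 16.98 (15.55 to 18.42) |

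The algebra gives 0/0/10, 7/7/7, 7/7/17 and 7/17/17. The coded row agrees with a predicted mean only where the relevant τ is zero.

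**4. The allowed departures.**

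- *Time effect dropped.* NOINT then leaves no fixed intercept, and the population line is forced through zero. Scenario D gives 10.37 ms (9.39 to 11.34) with NOINT and 16.82 ms (15.62 to 18.01) with an intercept (40 datasets).
- *Quadratic term kept.* With assumed coefficients 0.3 and -0.003 at Cmax 35, an unchanged row gives 0.3 × 35 = 10.5 ms. With the quadratic coefficient included it gives 10.5 - 0.003 × 35² = 6.8 ms.
- *ALPHA.* If the template is reused unchanged for HR, PR or QRS, the intervals are 1.645/1.960 = 0.839 of the required width, that is 16% too narrow.

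**The case against.** The strongest reply is that slope × Cmax is a legitimate quantity and probably the one intended. The objective and endpoint ask for ECG change in relation to concentration, and the concentration-related part answers that. SOLUTION prints the slope and every ATPTN coefficient. SAP 11.5 also plans by-time-point means with CIs, and outlier counts for subjects who "meet each of the following criteria at each day/time point". A uniform shift would therefore be seen. This stands as a limit on the consequence, but it does not reconcile the sentence and label with the row. It is also weaker for testosterone: slope × Cmax compares Cmax with zero concentration, and eligible men have screening testosterone above 150 ng/dL.

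Other points also stand in part:

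- The code block is the linear template, so the quadratic and ALPHA items are programming notes. The text already gives the CI level for HR, PR and QRS.
- Dropping the time effect is only a last resort.
- No document gives Tmax, so using the 4-hour ECG to represent peak leuprolide is an assumption.
- SAP 1 places the PK analysis in another plan, which may define the Cmax convention.
- The millisecond figures rest on invented inputs; only the algebra is general.

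None of these removes the mismatch.

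**Conclusion.** The concern holds. As written, the code gives a different quantity from the one the SAP text names. The discrepancy is exactly the weighted mean of the time-point effects, whatever the data. Its size in this trial cannot be derived from the documents; the 10 ms gaps above follow directly from assumed 10 ms time effects.

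The fault is minor and confined to the ECG report. The success criterion in SAP 9.1 (lower confidence bound for the Day 168 response rate above 90%) does not depend on it. It should be fixed before the ECG report is programmed, because the row will otherwise run without warning under a label it does not match.

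**What to change.** Choose one quantity and make sentence, label and code agree.

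- **Option 1, slope × Cmax.** Keep the row, label it as the concentration-related part of ΔECG at Cmax, and change the sentence in SAP 11.5 to match. This needs no choice of time point.
- **Option 2, predicted mean.** Add ATPTN coefficients that sum to 1 and state which time points they represent. For leuprolide, separate rows with coefficient 1 on Day 0 at 4 h and on Day 84 at 4 h would do. Four hours is the only post-injection ECG time on dosing days; state that it stands in for the peak. Equal weights are possible, but 3 of the 5 levels are not post-injection visits.

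In either case:

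- state which dose's mean Cmax replaces xx.x, or cite the PK plan if it says so, since protocol 7.4.3 determines Cmax after each dose;
- list the ATPTN levels;
- state the testosterone choice separately: no ECG is scheduled between Day 0 at 4 h and Day 28, while protocol 5.5 places the transient testosterone rise in the first week;
- if the quadratic term is kept, add its coefficient (xx.x squared); if concentration is transformed, transform xx.x too;
- if ATPTN is dropped, remove NOINT and, for a predicted mean, give the intercept coefficient 1;
- set ALPHA=0.05 for HR, PR and QRS.

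The cost is one decision and one sentence of SAP text or a few ESTIMATE lines. No new data are needed.

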5.5. Warning and Precautions

LMIS 25 mg contains the active pharmaceutical ingredient of leuprolide. Thus, the use of LMIS 25 mg may cause adverse events similar to the established AE profiles observed in the use of leuprolide acetate.

Leuprolide acetate has the following established significant AEs:

- Transient clinical testosterone flare reaction in men with prostate cancer
- Osteoporosis

Like other LH-RH analogs, leuprolide acetate causes a transient increase in the serum concentration of testosterone during the first week of treatment. This effect may cause subjects to experience a worsening of symptoms or an onset of new symptoms including bone pain, neuropathy, hematuria, or ureteral or bladder outlet obstruction. Long-term use of an LH-RH agonist has been reported to decrease bone mineral density which can increase the risk of osteoporosis and skeletal bone fractures.

Other reported adverse events of leuprolide acetate include hypogonadism, reduction in glucose tolerance, metabolic syndrome, anemia, and prolongation of the QT/QTc interval.

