7.3.6. Bone pain

Pain is a common problem for men with prostate cancer, but not all men will have pain. The most common cause of pain is because cancer has spread to the bones, but even that more than 25% of men don't have any pain. If cancer has spread to several other body organs, men often only have pain in a few of these organs.

Bone pain caused by cancer which has spread to the bones has a very specific feeling. Some subjects describe it as feeling similar to a toothache but in the bones, or like a dull aching or stabbing. Bone pain will be assessed by subject visual assessment scales (VAS) ranging from 1 (no pain) to 10 (worst possible pain) (see [Appendix II](#)), and will be evaluated at baseline (Day 0, pre dose), Day 1, Day 7 ± 1 day (week 1), Day 14 ± 1 day (week 2), Day 28 ± 1 day (week 4), Day 56 ± 3 days (week 8), Day 84 ± 1 day (pre dose, week 12), Day 112 ± 3 days (week 16), Day 140 ± 3 days (week 20), and Day 168 ± 5 days (week 24, EOS/ET).

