7.3.7. Urinary signs and symptoms

Urinary signs and symptoms will be assessed using the International Prostate Symptom Score (I-PSS) including 7 questions (See [Appendix III](#)). Based on the total score from answering the 7 questions, the urinary symptom can be assessed as: 1-7 (Mild), 8-19 (Moderate), 20-35 (Severe). Urinary signs and symptoms will be evaluated at baseline (Day 0, pre dose), Day 1, Day 7 ± 1 day (week 1), Day 14 ± 1 day (week 2), Day 28 ± 1 day (week 4), Day 56 ± 3 days (week 8), Day 84 ± 1 day (pre dose, week 12), Day 112 ± 3 days (week 16), Day 140 ± 3 days (week 20), and Day 168 ± 5 days (week 24).

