Individual subject ECOG performance status will be listed in Listing 16.4.4. The ECOG performance status will be summarized descriptively as Table 14.1.2.

Local Injection Site Reaction

Individual subject Local Injection Site Reaction will be listed in Listing 16.4.5. The local injection site reaction as recorded by Grade 0 (None), Grade 1 (Mild), Grade 2 (Moderate) and Grade 3 (Severe) will be summarized descriptively as count and percentage as Table 14.3.9.

Bone pain and urinary sign and symptoms (I-PSS)

Individual subject Bone pain and urinary sign and symptoms will be listed in Listing 16.4.6~ Listing 16.4.8. The summary results of VAS scale for bone pain measurement at baseline, EOS/ET Visit

Statistical Analysis Plan

and the change from baseline will be summarized descriptively in Table 14.3.10.1. Also, the change from baseline to EOS/ET visit will be tested by paired t-test or Wilcoxon signed-rank test at a significance level of 0.05. The urinary sign and symptoms at baseline and EOS/ET Visit will be summarized descriptively as Table 14.3.10.1. The transition status for urinary sign and symptoms by each scale* will be presented as Table 14.3.10.2. The quality of life will be presented as Table 14.3.10.3.

*For Urinary signs and symptoms Q1-Q6: 0 - None, 1 - Less than 1 time in 5, 2 - Less than half the time, 3 - About half the time, 4 - More than half the time, and 5 - Almost always.

For Urinary signs and symptoms Q7: 0 - None, 1 - 1 time, 2 - 2 times, 3 - 3 times, 4 - 4 times, 5 - 5 or more times.

For Urinary signs and symptoms quality of life: 0 - Delighted, 1 - Pleased, 2 - Mostly Satisfied, 3 - Mixed, 4 - Mostly Dissatisfied, 5 - Unhappy, 6 - Terrible

Unscheduled Assessments

The unscheduled assessment will be listed in Listing 16.4.9.

Telephone Contact

The telephone contact information will be listed in Listing 16.4.10.

12.COMPUTER METHODS

All statistical analyses will be conducted using SAS[®] software, Version 9.3 of the SAS System for Windows 7. Copyright[©] 2013 SAS Institute Inc. SAS and all other SAS Institute Inc. product or service names are registered trademarks or trademarks of SAS Institute Inc., Cary, NC, USA.

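### Bone pain VAS and I-PSS scores have specified summaries only at baseline and EOS/ET, so the plan cannot show early, transient worsening in the testosterone flare window

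*SAP*

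**What the plan says.** **The risk.** Protocol 5.5 lists testosterone flare as an established significant adverse event of leuprolide acetate and expects LMIS 25 mg to behave similarly. It says that "leuprolide acetate causes a transient increase in the serum concentration of testosterone during the first week of treatment" and that this may bring "worsening of symptoms or an onset of new symptoms including bone pain, neuropathy, hematuria, or ureteral or bladder outlet obstruction".

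**The data.** Protocol 7.3.6 says bone pain "will be evaluated at baseline (Day 0, pre dose), Day 1, Day 7" and then on Days 14, 28, 56, 84, 112, 140 and 168. Protocol 7.3.7 gives the same days for I-PSS, and the schedule tables in both documents agree. SAP 3.3 lists change in VAS, and change in urinary symptoms with total score, as secondary safety endpoints. Safety is also part of the primary objective.

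**The analysis.** For VAS, SAP 11.5 specifies "The summary results of VAS scale for bone pain measurement at baseline, EOS/ET Visit" and the change from baseline, and then "the change from baseline to EOS/ET visit will be tested by paired t-test or Wilcoxon signed-rank test". For I-PSS it says "The urinary sign and symptoms at baseline and EOS/ET Visit will be summarized descriptively" and specifies no change score and no test. It adds an I-PSS transition table (14.3.10.2) and a quality-of-life table (14.3.10.3), neither with stated visits. Individual values go to Listings 16.4.6 to 16.4.8. Protocol 10.5 names the same two time points. The protocol synopsis (X.5, item 10) promises a summary of change in both scales with a paired test, but names no post-baseline visit.

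**The concern.** The documents place flare symptoms in the first week and measure two relevant scales within it. The specified score summaries then compare Day 0 with the end of study, nominally Day 168. A subject whose bone pain rises on Day 1 or Day 7 and settles by Day 168 looks unchanged in every specified VAS summary. A programmer who follows SAP 11.5 exactly will produce no table showing how many subjects worsened early, or by how much. That is a question a safety reader of an LH-RH agonist trial would ask, and the answer would sit in the database without being tabulated.

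**Working it through.** The plan states no figure on this point, so there is none to reproduce. The check sets the collection schedule against the specified output.

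**1. Assessments collected per scale** (protocol 7.3.6, 7.3.7 and Tables 1a and 1b)

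| | Days | Count |
|---|---|---|
| Baseline | 0 | 1 |
| First week | 1, 7 | 2 |
| Rest of first four weeks | 14, 28 | 2 |
| Later | 56, 84, 112, 140 | 4 |
| EOS | 168 | 1 |

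Post-baseline assessments: 2 + 2 + 4 + 1 = 9.

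**2. Assessments with a specified score summary** (SAP 11.5 and protocol 10.5)

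Of the nine, only Day 168 (EOS/ET) is named. Without a specified summary: 9 − 1 = 8, or 8/9 = 89%. Both first-week assessments are among the eight. The summarised visit falls 168 − 7 = 161 days after the end of the flare window.

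**3. Volume left to listings**

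SAP 4.4 reports 144 subjects enrolled. If all attended every visit, the by-subject listings would hold 144 × 8 = 1,152 VAS values with no specified summary, of which 144 × 2 = 288 come from Days 1 and 7. These are upper limits, because attendance is not known.

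**4. Could the two-visit wording be shorthand for all visits?**

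The SAP names the visits when it wants by-visit output. SAP 9.2 asks for change in PSA and LH at scheduled visits. The ECG report part of SAP 11.5 asks for results and changes at every visit and time point, plus categorical summaries at the post-dose maximum or minimum. The VAS and I-PSS text has no such wording. SAP section 1 says the SAP governs where it differs from the protocol, and protocol 10.5 does not differ.

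**5. Does other output fill the gap?**

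- TEAE tables (SAP 11.1) are by system organ class, preferred term, severity and relationship. None is by time since dose.
- Tables 14.3.10.2 and 14.3.10.3 concern I-PSS and quality of life, so they could not cover VAS even if produced by visit.
- A subject who stops in the first weeks has EOS procedures that day, so an early score enters the EOS/ET column. That mixes early and late values and does not describe the flare.

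**The case against.** The strongest reply is that the plan is consistent and conventional. The protocol and SAP agree. Baseline against EOS/ET is also the SAP's pattern for laboratory data (11.3), vital signs (11.4) and the routine ECG summary (11.5). These are secondary safety endpoints in an uncontrolled study. Subjects at risk of spinal cord compression or urinary obstruction are excluded, which should make severe flare symptoms less frequent. Investigators ask about adverse events at every visit. All of this is true. It lowers the stakes but does not supply the missing summary: a listing gives no frequency or size of worsening, and a rise in a score need not be reported as an adverse event.

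Several stronger readings are tempting, and the documents do not support them:

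- **That early harm feeds no table at all.** Symptoms reported as adverse events enter the TEAE tables, and the scores are listed. What is missing is a specified summary of the early scores.
- **That the planned analysis can show only benefit or no change.** The synopsis makes all tests two-sided, so worsening at EOS/ET could appear.
- **That early I-PSS output is excluded.** The visits of Tables 14.3.10.2 and 14.3.10.3 are unstated, and no table shells are available here. By-visit I-PSS output is unspecified, not ruled out.
- **That all four assessments through Day 28 lie in the flare window.** Protocol 5.5 says the first week, so only Days 1 and 7 do.
- **That the early visits were scheduled in order to detect flare.** Protocol 7.3.6 explains bone pain by metastasis and does not mention flare.
- **That I-PSS is as informative as VAS.** The form in Appendix III asks about the past month, so Day 1 and Day 7 answers largely describe the time before dosing.

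**Conclusion.** The point holds as a gap between what is measured and what is summarised. Eight of nine post-baseline assessments of each scale have no specified score summary, including both assessments in the first-week window that the protocol itself names. The specified summaries can show a difference at the end of study in either direction, but not an early worsening that resolves. The gap is clearest for VAS, where no other specified table could cover it. For I-PSS it is partly an unstated table layout. Primary efficacy is unaffected.

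This conclusion rests on reading SAP 11.5 literally, which its by-visit wording for PSA, LH and ECG supports. It also assumes that protocol 5.5's description of leuprolide acetate applies to LMIS 25 mg, as that section says it may. How often the scores will worsen early cannot be judged from the documents. The change should be made, since the data already exist.

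**What to change.** In SAP 11.5:

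1. Summarise change from baseline descriptively at each scheduled visit for VAS and for I-PSS total score.
2. For VAS, add the maximum increase from baseline through Day 28, with Days 1 and 7 shown separately, and the number and percentage of subjects with any increase. The documents give no threshold in centimetres for a meaningful increase, so none is proposed.
3. State which visits Tables 14.3.10.2 and 14.3.10.3 cover.
4. Label early I-PSS results as supportive because of the one-month recall.
5. Before tabulating change, reconcile the VAS lower anchor. Protocol 7.3.6 runs the scale from 1 for no pain, while Appendix II measures a 10 cm line from its left end, which implies 0. If the two conventions were mixed within a subject, an unchanged pain-free state would appear as a one-unit change.

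The cost is two or three extra descriptive tables, with no new data and no added visits. There is no control arm, so the tables cannot attribute a change to the drug. A count of any increase, and a maximum taken over several visits, will both include ordinary measurement variation. They should be read beside the by-visit means and without significance tests.
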